31-Jul-2018	Prior to DB lock for primary analysis (group 3)	Creation of amendment 2	
Addition of subgroup for CNS metastases
 
Study documents' versions
 
Cut-off date for Group 3 primary analysis
 
Definition of a FAS and safety subset
 
Definition of first-line patients in Group 4
 
Revised the exclusion of Group 2 from efficacy summaries
	
2.5.1.2 Statistical hypothesis, model, and method of analysis – Phase Ib: Updated that the posterior distribution of the model parameters and of DLT rates will be presented for the model at the time of MTD declaration and at the end of the Phase Ib. Added that corresponding graphs will be produced.
 
2.5.2.2.1 Group 1: A typo in the interval for moderate anti-tumor activity was corrected.
 
2.5.2.4 Supportive analyses: Clarified that reasons for unknown BOR will be presented for both local and BIRC assessment results.
 
2.8.1 Adverse events (AEs): Update to table SAE with fatal outcome.
 
6 References: Update to reference Kunzmann (2016).
 
Corrections of typos.
 
2.2.5.2 Subjects with CNS metastases: the definition of CNS metastases was added.
 
1 Introduction: versions of Study specification document and Case Retrieval Sheets were updated.
 
2.1.2 Reports: the primary analysis of Group 3 subjects will be performed for internal decision-making.
 
2.2.3 Subsets for the primary analysis of Group 3 subjects: FAS – 1L subjects and safety set – 1L subjects were defined.
 
2.2.5.3 Line of therapy: a new derivation for first-line status of subjects in Group 4 was added.
 
2.3.1 Basic demographic and background data, disease history: grouping of metastatic sites (for in-text table) was added.
 
2.7.1 Secondary endpoints: removed the sentence excluding Group 2. Despite the low number, Group 2 subjects will be included in tables.

Date	Time point	Reason for update	Outcome for update	Section and title impacted (Current)
19-Sep-2018	Prior to DB lock for primary analysis (group 3)	Request from upper management	Clarification Amendment 3: Adding a summary of time to first dose modification. Study document versions.	Several sections: Minor clarifications. 2.4.1, Study treatment / compliance: Derivation rule for interruptions was updated. Analysis of time to first dose modification was added. 1 Introduction: version of Study specification document was updated.
12-Sep-2020	Prior to DB lock for final analysis	New version of Novartis Hepatotoxicity Guideline; Covid-19-related protocol deviations.	Amendment 4: Addition of outputs for Covid-19 related PDs. Modified analysis of liver function parameters. Revised to only present the required analyses and specifications for the final CSR.	All sections: Text related to analyses other than for the final CSR were removed. Per program standard 'c-MET' was replaced by 'MET'. The list of abbreviations was updated. 1 Introduction: Versions of study documents were updated. A paragraph about the impact of the COVID-19 pandemic was added. 2.1.4 General definitions: Minor clarification for baseline definition. 2.2.2 Analyses by subgroup: The specific analyses were deleted to avoid having the same information in several sections. Reference is made to the sections 2.7, 2.8 and 2.11.6. 2.3 Subject disposition, demographics and other baseline characteristics: paragraphs for baseline data that will not be analyzed and presented again were removed. 2.3.3 Subject disposition: Analysis of COVID-19 related PDs was added. 2.4.1 Study treatment / compliance: The summary of individual dose interruptions was removed. The specification for dose interruptions ongoing at the time of the data cut-off was changed (not expected for the final analysis). Prior anti-neoplastic therapies will not be reported again and the paragraphs were removed. 2.5.1 Phase Ib: No analysis of the primary objective for Phase Ib will be done and the details were deleted.

Date	Time point	Reason for update	Outcome for update	Section and title impacted (Current)
				
2.5.2.2 Statistical hypothesis, model, and method of analysis – Phase II Groups 1, 2, and 3: The Bayesian estimation of the ORR will not be done for the Final CSR; the related specifications were deleted.
 
2.5.2.3 Handling of missing values/censoring/discontinuations – Phase II Groups 1, 2, and 3: Additional specifications of censoring for new anti-cancer therapy were added.
 
2.7.2 Statistical hypothesis, model, and method of analysis (Censoring pattern of OS): reason for death will not be summarized in the OS table, only the number of deaths and censorings.
 
2.8.3 Laboratory data: Shift tables for lab parameters will not be prepared for the final CSR. The analysis of liver function parameters was modified to align with the current Novartis Hepatotoxicity Guideline.
 
2.8.4.1 ECG: Change from baseline in ECG parameters by time point was added.
 
2.8.4.3 ECOG performance status: Summary of performance status by time point was removed.
 
2.11.5 Derivation of resistance mechanism subgroups for Phase Ib subjects: The subgroup categories for T790M & MET status crossed were updated to also include the missing and the individual categories.
 
2.11.6 Biomarker analysis: The biomarker summary by response status (BOR) for MET expression was changed to IHC category (instead of H-score). A summary of PFS by biomarker categories (GCN and IHC) was added. Corresponding graphical displays will be generated for the Phase II treatment groups only (BOR and PFS).
 
5.1.3 Other imputations: the imputation rules for start dates of post-treatment antineoplastic medications were specified in more detail (Table 5-3).
 
6 References: Typo correction in reference Collett D (1994).

Date	Time point	Reason for update	Outcome for update	Section and title impacted (Current)
06-Nov-2020	Prior to DB lock for final analysis	Update of the last contact date definition	Amendment 5: Update of the last contact date for OS	Update Table 2-1 Last contact date data sources. Date of assessment collected on the "Survival information" eCRF will be considered for last contact date, this is aligned with eCRF completion guidelines (last known date patient alive is not required if subject is reported to be alive)
25-Nov-2021	Prior to DB lock for interim CSR analysis	Cancellation of final analysis and CSR	The previous SAP (amendment 5) for the final CSR analysis will be retired in CREDI	Whole document
25-Nov-2021	Prior to DB lock for interim CSR analysis	Cancellation of final analysis and CSR	Amendment 5 (replacing the retired amendment 5)	List of abbreviations: abbreviations were updated (removed/added). 1 Introduction: Versions of study documents were updated. A paragraph to explain the canceled final CSR was added. A paragraph to explain the purpose of the current SAP was added. The paragraph on COVID-19 pandemic related protocol deviations was moved and updated. 1.1.2 Phase II part: Final CSR was changed to interim CSR. 2.1.1 Data included in the analysis: The paragraph was updated to include a separate cut-off date for efficacy analyses (to be used as censoring date). 2.1.2 Reports: Final CSR was changed to interim CSR. 2.1.4 General definitions: The paragraph on last contact date was updated. 2.2.2.1 Resistance mechanism to EGFR TKI treatment: Update of the derivation of biomarker subgroup status for Phase II subjects (based on biomarker results instead of IRT data). 2.3.3 Subject disposition: An additional analysis of COVID-19 related protocol deviations was added (per Novartis internal guidance).

Date	Time point	Reason for update	Outcome for update	Section and title impacted (Current)
				
2.5.1 Phase Ib: Final CSR was changed to interim CSR.
 
2.5.2.2 Statistical hypothesis, model, and method of analysis – Phase II Groups 1, 2, and 3: Final CSR was changed to interim CSR.
 
2.7.1 Secondary endpoints: the efficacy cut-off date was added (TTR, PFS, OS).
 
2.7.3 Handling of missing values/censoring/discontinuations: the efficacy cut-off date was added (PFS, OS).
 
2.9 Pharmacokinetic endpoints: Final CSR was changed to interim CSR.
 
2.11.1 Introduction: Final CSR was changed to interim CSR.
 
2.11.4 General data handling and preprocessing: Updated the scope of Table 2-9 to Phase II. Clarified, that the biomarker test method needs to match the protocol requirements to be considered to derive resistance mechanism subgroups.
 
2.11.5 Derivation of resistance mechanism subgroups: Removed “for Phase Ib subjects” from the subsection title. Also added Phase II in the text. Presentation of the T790M and MET status subgroups was changed to tabular format.
 
4 Change to protocol specified analyses: A paragraph header was added for each change.
 
5.1.1 Investigational drug: Final CSR replaced by interim CSR.
 
6 References: References were updated.
 
General: Correction of typos.

CTC	Common Toxicity Criteria
CTCAE	Common Terminology Criteria for Adverse Events
DAR	Dosage Administration Record
DBL	Database Lock
DCR	Disease Control Rate
DILI	Drug-Induced Liver Injury
DLT	Dose Limiting Toxicity
DOR	Duration Of Response
FAS	Full Analysis Set
ECG	Electrocardiogram
ECOG	Eastern Cooperative Oncology Group
eCRF	Electronic Case Report Form
eDISH	Evaluation of Drug-Induced Serious Hepatotoxicity
EGFR	Epidermal Growth Factor Receptor
EOT	End of Treatment
EudraCT	European Union Drug Regulating Authorities Clinical Trials
EWOC	Escalation With Overdose Control
FDA	Food and Drug Association
FISH	Fluorescence In Situ Hybridization
GCN	Gene copy number
HGLT	High Level Group Terms
HLT	High Level Terms
HR	Heart Rate
IA	Interim analysis
IHC	Immuno-Histo-Chemistry

IRT	Interactive Response Technology
MedDRA	Medical Dictionary for Drug Regulatory Affairs
MRI	Magnetic Resonance Imaging
MTD	Maximum Tolerated Dose
NGS	Next Generation Sequencing
NMQ	Novartis MedDRA Query
NSCLC	Non-Small Cell Lung Cancer
ORR	Overall Response Rate
OS	Overall Survival
OSO	Oncology Standard Outputs
PCR	Polymerase Chain Reaction
PDI	Planned dose intensity
PDS	Programming Datasets Specifications
PFS	Progression-Free Survival
PK	Pharmacokinetics
PPS	Per-Protocol Set
PR	Partial Response
PS	Performance Status
PT	Preferred Term
QTcF	Corrected QT interval using Fridericia correction
RECIST	Response Evaluation Criteria in Solid Tumors
RDI	Relative dose intensity
RP2D	Recommended Phase 2 Dose
SAP	Statistical Analysis Plan
SAE	Serious Adverse Event
SMQ	Standard MedDRA Query
SOC	System Organ Class
SSD	Study Specification Document
TA	Tumor assessment
TBL	Total bilirubin
TFLs	Tables, Figures, Listings
TKI	Tyrosine Kinase Inhibitor
TTP	Time To Progression
TTR	Time To Response
ULN	Upper Limit of Normal
UNK	Unknown
WBC	White Blood Cell(s)
WHO	World Health Organization
WHO DRL	WHO Drug Reference Listing

1 Introduction

This statistical analysis plan (SAP) describes the analyses for the final Clinical Study Report (CSR) of study CINC280X2105C, a phase Ib/II, multicenter, open-label study of EGF816 in combination with INC280 in adult patients with EGFR mutated non-small cell lung cancer.

[REDACTED]

[REDACTED]

[REDACTED]

[REDACTED]

[REDACTED]

[REDACTED]

COVID-19 pandemic

In addition to the study protocol deviation (PD) terms, Novartis has defined 6 new protocol deviations related to the COVID-19 pandemic and the corresponding relationship (health status related vs. site lockdown, patient concerns, drug supply issue etc.) in line with “FDA Guidance on Conduct of Clinical Trials of Medical Products during COVID-19 Public Health Emergency” [Food and Drug Administration 2020] and “Guidance on the management of clinical trials during the COVID-19 (coronavirus) pandemic” [European Medicines Agency 2021]. The following deviations related to the COVID-19 pandemic will be summarized.

- Missing visits
- Changes in procedures and assessments

- Planned visits not done at sites
- Changes in drug supply method
- Treatment not given
- Subject discontinuation due to COVID-19 situation

A cross-tabulation of COVID-19 related PD vs. relationship will also be produced.

Based on a preliminary assessment, the impact on the efficacy and subjects' safety is minimal and no other analyses are planned.

1.1 Study design

This is a phase Ib/II, multi-center, open-label study in adult subjects with EGFR mutated non-small cell lung cancer starting with a Phase Ib dose escalation part followed by a Phase II part.

There is no randomization process, as all subjects will receive the same study treatment.

1.1.1 Phase Ib part

[figure not shown]
In the Phase Ib part at least 18 subjects who have progressed on previous EGFR TKI treatment (e.g. post erlotinib, gefitinib or afatinib) will be enrolled. An adaptive Bayesian Logistic Regression Model (BLRM) with escalation with overdose control (EWOC) will guide the dose escalation to determine the maximal maximum tolerated dose (MTD) or recommended Phase II dose (RP2D). Before a drug dosage can be declared to be the MTD or RP2D, at least six subjects should have been treated at that dosage.

The incidence of dose limiting toxicities (DLTs) is the primary endpoint for the Phase Ib part.

1.1.2 Phase II part

Once the MTD or RP2D has been declared, approximately 115 additional subjects will be enrolled in the Phase II part, as shown in Figure 1-1, in order to assess the preliminary anti-tumor activity of EGF816 in combination with INC280.

Figure 1-1 Study design

In the Phase II Group 1 (EGFRmut, any T790M, any MET, 2/4L antineoplastic, EGFR TKI resistant), subjects with a previously documented EGFRmut^{L858R/ex19del} NSCLC, who develop resistance to EGFR TKI treatment (e.g. post erlotinib, gefitinib or afatinib) will be enrolled and assigned according to their acquired resistance mechanism to one of four sub-groups:

- sub-group 1a: EGFRmut^{L858R/ex19del} NSCLC with acquired mutation T790M (T790M+, MET dysregulation-).
- sub-group 1b: EGFRmut^{L858R/ex19del} NSCLC with demonstrated MET dysregulation (T790M-, MET dysregulation+).
MET dysregulation is defined as either
 - a. IHC 3+ (defined as ≥ 50% of cells staining with high intensity) and/or
 - b. MET gene copy number ≥ 4
- sub-group 1c: EGFRmut^{L858R/ex19del} NSCLC with evidence of both acquired T790M and MET dysregulation (T790M+, MET dysregulation+).
- sub-group 1d: EGFRmut^{L858R/ex19del} NSCLC with MET dysregulation below the levels for sub-group b (T790M-, MET dysregulation-).

At least 40 subjects will be enrolled in the Phase II part Group 1 with a minimum of 20 subjects harboring the T790M mutation among sub-groups 1a and 1c, and a minimum of 20 subjects who do not harbor the T790M mutation among sub-groups 1b and 1d.

The Phase II part Group 2 (EGFRmut, de novo T790M, any MET, 1/3L antineoplastic, EGFR TKI naïve) will enroll approximately 5 NSCLC subjects who are EGFR inhibitor treatment (including anti-EGFR monoclonal antibodies) naïve and harbor T790M de novo mutation. The subjects may harbor or may not harbor an EGFR activating mutation (L858R and/or ex19del)

in addition to the EGFR T790M mutation of resistance. The incidence of de novo T790M mutation is rare (~1%). The enrollment in Group 2 will stop once the enrollment in the other groups is completed to allow for completion of recruitment within a reasonable timeframe.

In the Phase II Group 3 (EGFRmut, T790M negative, any MET, 1L antineoplastic), a minimum of 40 subjects with documented EGFRmut^{L858R/ex19del} NSCLC, who have never received any systemic antineoplastic therapy will be enrolled.

In the Phase II Group 4 (EGFRmut, any T790M, any MET, 1L (treatment naïve) or 2–3L antineoplastic) approximately 30 subjects, with documented EGFRmut NSCLC, who have never received any systemic antineoplastic therapy or have failed a maximum of 2 lines of antineoplastic therapies for advanced disease will be enrolled. Group 4 subjects will take study treatment with food (unrestricted meal type) whilst subjects from all other groups will take the study treatment under fasting conditions. Approximately 10 subjects who are treatment-naïve for the advanced setting should be enrolled in Group 4 in order to collect some safety information on this subject population.

Note for Phase II all groups: subjects who have received no more than 1 cycle of systemic antineoplastic therapy in the advanced setting are allowed.

Treatment-naïve subjects should be enrolled in Group 3 as priority before being enrolled into Group 4. De novo T790M subjects should be enrolled into Group 4 as priority before being enrolled into Group 2.

Overall response rate (ORR), as assessed by local investigators review of tumor response and using RECIST 1.1 criteria, is the primary endpoint in the Phase II of the study.

One interim analysis was conducted for Phase II Group 3 (EGFRmut, T790M negative, any MET, 1L antineoplastic) when 21 evaluable subjects had completed at least 4 cycles of treatment or discontinued treatment prior to that time.

The primary analysis was conducted based on all subjects' data of the Phase Ib dose escalation part and the Phase II part up to the time when all treated subjects had completed 6 cycles (about 6 months) of treatment. The primary analysis data were summarized in the primary CSR.

1.2 Study objectives and endpoints

Table 1-1 Study protocol objectives and related endpoints

Objective	Endpoint
Primary	
Phase Ib part: To estimate the MTD or RP2D of EGF816 in combination with INC280	Incidence of DLTs
Phase II part: To estimate the preliminary anti-tumor activity of EGF816 in combination with INC280 (Groups 1, 2 and 3)	Overall response rate (ORR) per RECIST v1.1 based on investigator's assessment
To characterize the safety and tolerability of EGF816 in combination with INC280 when taken with food (Group 4)	Safety: Incidence and severity of AEs and SAEs Tolerability: Dose interruptions, reductions and dose intensity

Objective	Endpoint
Secondary	
Phase Ib/II parts: To characterize the safety and tolerability of EGF816 in combination with INC280	Safety: Incidence and severity of AEs and SAEs, including changes in hematology and chemistry values, vital signs and ECGs Tolerability: Dose interruptions, reductions and dose intensity
Phase Ib part: To evaluate the preliminary anti-tumor activity of EGF816 in combination with INC280	ORR, PFS, time to response (TTR), duration of response (DOR) and disease control rate (DCR) based on investigator's assessment and, overall survival (OS)
Phase II part: To evaluate the preliminary anti-tumor activity of EGF816 in combination with INC280	PFS, TTR, DOR, DCR and ORR (Group 4 only) based on investigator's assessment and OS (all Phase II groups)
Phase Ib/II parts: To characterize the PK of EGF816 and INC280 when given in combination under fasted state or with food	Plasma concentration vs time profiles Plasma PK parameters of EGF816 and INC280
[REDACTED]	[REDACTED]
[REDACTED]	[REDACTED]
[REDACTED]	[REDACTED]

The protocol foresees that imaging data will be centrally collected, checked for quality and stored for possible independent review by an imaging CRO designated by Novartis. Meanwhile it was decided to have the independent review performed for subjects treated at the RP2D (Phase Ib and Phase II) and to analyze the results of the central Blinded Independent Review Committee (BIRC) evaluations as supportive for the primary endpoint and secondary efficacy endpoints.

2 Statistical methods

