2.4 Treatments (study treatment, concomitant therapies, compliance)

2.4.1 Study treatment / compliance

Duration of exposure, actual cumulative dose, dose intensity (DI) and relative dose intensity (RDI) will be summarized by treatment group, separately for each component of study treatment. Duration of exposure will also be presented for the study treatment. Duration of exposure will be categorized into time intervals; frequency counts and percentages will be presented for the number of subjects in each interval. The number (%) of subjects who have dose reductions or interruptions, and the reasons, will be summarized by treatment group.

Subject level listings of all doses administered on treatment along with dose change reasons will be produced.

The safety set will be used for all summaries and listings of study treatment.

Duration of exposure to study treatment

Duration of exposure to study treatment is considered by taking into account the duration of exposure to the investigational drugs:

Duration of exposure to study treatment (days) = (last date of exposure to study treatment) – (date of first administration of study treatment) + 1.

The last date of exposure to study treatment is the latest of the last dates of exposure to any of the investigational drugs (see [Section 2.1.4](#)).

Summary of duration of exposure to study treatment will include categorical summaries and continuous summaries (i.e. mean, standard deviation etc.) using the time unit weeks. The following time intervals will be presented: ≤ 4 weeks, $4 < \leq 8$ weeks, $8 < \leq 12$ weeks, $12 < \leq 16$ weeks, $16 < \leq 24$ weeks, $24 < \leq 32$ weeks, $32 < \leq 52$ weeks, $52 < \leq 78$ weeks and >78 weeks.

Duration of exposure to investigational drugs

Duration of exposure to investigational drug (days) = (last date of exposure to investigational drug) – (date of first administration of investigational drug) + 1.

The last date of investigational drug exposure is defined as the date of last administration of a non-zero dose of the drug (see [Section 2.1.4](#)).

For subjects who did not take any drug, the duration of drug exposure is by definition equal to zero.

The exposure duration may include periods of temporary interruption. If a subject is still on treatment at the time of data cut-off, the end date of investigational drug/study treatment will be replaced by the data cut-off date and the above calculations will be applied.

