2.5.2 Phase II

The primary objective of the Phase II part is to estimate the preliminary anti-tumor activity of EGF816 in combination with INC280 measured by ORR determined by the Investigators' assessment in accordance with RECIST 1.1 in each of the groups 1 to 3. In Group 4 the primary

objective is to characterize the safety and tolerability of EGF816 in combination with INC280 when taken with food.

The primary objective for the Phase II was analyzed in the primary analysis and reported in the [primary CSR]. The analyses described below will be updated including the data collected for subjects ongoing at the cutoff date for the primary analysis.

2.5.2.1 Primary endpoint – Phase II Groups 1, 2, and 3

ORR is defined as the proportion of subjects with best overall response (BOR) of complete response (CR) or partial response (PR) according to RECIST 1.1 (see [CSP Appendix 1]). ORR will be calculated based on the FAS using local investigators review of tumor assessment data. Tumor assessments performed before the start of any further antineoplastic therapy (i.e. any additional secondary antineoplastic therapy or surgery) will be considered in the assessment of BOR. Radiotherapy to the bone or central nervous system (CNS), and surgical resection of CNS metastases as well as palliative bone radiotherapy is allowed as per protocol, and will not be considered in determining antineoplastic therapy usage.

The ORR will be estimated by group or sub-group as assigned based on baseline mutation status and prior systemic antineoplastic therapy. The following groups will be considered (see also Section 1.1.2).

- Group 1, EGFRmut, any T790M, any MET, 2/4L antineoplastic, EGFR TKI resistant
- Group 2, EGFRmut, de novo T790M, any MET, 1/3L antineoplastic, EGFR TKI naïve
- Group 3, EGFRmut, T790M negative, any MET, 1L antineoplastic first line

Best overall response

BOR is the best response recorded from the start of the treatment until documented radiological disease progression/recurrence. However, any assessments taken more than 30 days after the last dose of study treatment will not be included in the best overall response derivation.

The study requires that for a partial response (PR) or complete response (CR) changes in tumor measurements must be confirmed by repeat assessments performed no less than 4 weeks after the criteria for the response are first met.

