[figure not shown]
The protocol allows radiotherapy to the bone or central nervous system (CNS), and surgical resection of CNS metastases as well as palliative bone radiotherapy (that is, these will not lead to censoring).

Derivation of new anti-cancer therapy

To determine the use of new anti-cancer therapy, data entered in the following CRFs will be considered [REDACTED]:

- Antineoplastic Therapy Since Discontinuation of Study Treatment – Medication,
- Antineoplastic Therapy Since Discontinuation of Study Treatment – Radiotherapy,
- Antineoplastic Therapy Since Discontinuation of Study Treatment – Surgery.

In addition certain therapies entered in the CRF Prior and Concomitant Medications (domain CM) will be considered, if they were started after start of study treatment.

2.5.2.5 Primary endpoint – Phase II Group 4

Frequencies of treatment-emergent AEs will be calculated to characterize the safety and tolerability of the study treatment. The Safety Set will be used for summary tables.

2.5.2.6 Statistical hypothesis, model, and method of analysis – Phase II Group 4

Adverse events will be analyzed as described in the section on safety analysis, [Section 2.8.1](#).

2.5.2.7 Handling of missing values/censoring/discontinuations – Phase II Group 4

Summary tables for AEs will include events collected in the on-treatment period. If dates are incomplete and no clear assignment to pre-, on-, or post-treatment period can be made, then on-treatment will be assumed (see [Section 5.1.2](#)).

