2.8.1 Adverse events (AEs)

Coding and grading of AEs

Adverse events are coded using the Medical dictionary for regulatory activities (MedDRA) terminology. The grading is done according to the Common Terminology Criteria for Adverse Events (CTCAE). See [Section 5.2](#) in the appendix for further details.

AE summaries

AE summaries will include all AEs occurring during the on-treatment period (see [Section 2.1.4](#)). All AEs collected in the AE eCRF page will be listed along with the information collected on those AEs, e.g. AE relationship to study treatment, AE outcome etc. AEs with start date outside of the on-treatment period will be flagged in the listings.

AEs will be summarized by number and percentage of subjects having at least one AE, having at least one AE in each primary system organ class (SOC) and for each preferred term (PT) using MedDRA coding. A subject with multiple occurrences of an AE will be counted only once in the respective AE category. A subject with multiple CTCAE grades for the same preferred term will be summarized under the maximum CTCAE grade recorded for the event. AE with missing CTCAE grade will be included in the 'All grades' column of the summary tables.

In AE summaries, the primary system organ class will be presented alphabetically and the preferred terms will be sorted within primary SOC in descending frequency. The sort order for the preferred term will be based on their frequency in the 'All subjects' column combining subjects from Phase Ib and Phase II.

The following adverse event summaries will be produced:

- Overview of adverse events and deaths
- AEs regardless of study treatment relationship (including CTC grade 3/4)
- AEs suspected to be study treatment related (including CTC grade 3/4)
- AEs regardless of study treatment relationship leading to discontinuation of study treatment
- AEs suspected to be study treatment related leading to discontinuation of study treatment
- AEs regardless of study treatment relationship requiring dose adjustment or study treatment interruption
- SAEs regardless of study treatment relationship
- SAEs suspected to be study treatment related
- SAEs with fatal outcome

In addition, tables required for ClinicalTrials.gov and EudraCT will be provided (see [Section 2.8.1.2](#)).

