2.8.1.1 Adverse events of special interest / grouping of AEs

An adverse event of special interest (AESI) is a grouping of adverse events that are of scientific and medical concern specific to the compound INC280 and/or EGF816. These groupings are

defined using MedDRA terms, standardized MedDRA queries (SMQs), high level group terms (HGLTs), high level terms (HLTs) and PTs. Customized SMQs (Novartis MedDRA queries, NMQ) may also be used. A NMQ is a customized group of search terms which defines a medical concept for which there is no official SMQ available or the available SMQ does not completely fit the need. It may include a combination of single terms and/or an existing SMQ, narrow or broad.

The adverse events of special interest to be monitored for INC280 and for EGF816 are specified in the respective electronic Case Retrieval Sheet (eCRS). [REDACTED]

The most recent version of the eCRS at the time of DBL or data snapshot will be used. The codes of the search terms related to the AESIs will be used to generate outputs. The eCRS version will be included in a footnote of the AESI tables.

For each specified AESI, the number and percentage of subjects with at least one event of the AESI occurring during the on-treatment period will be summarized (in separate tables for INC280 and EGF816).

Summaries of these AESIs will be provided by treatment groups, (specifying grade, SAE, relationship, leading to treatment discontinuation, leading to dose adjustment/interruption, hospitalization, death etc.).

A listing of all grouping levels down to the MedDRA preferred terms used to define each AESI will be generated.

[REDACTED]

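### Group 4's primary AE analysis, and the AE, AESI, dose-reduction and interruption tables in every group, are crude percentages over an open-ended window, so for events that accrue over time they mix event risk with treatment duration

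*SAP*

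**What the plan says.** Table 1-1 (Section 1.2) sets the Group 4 primary endpoint as "Safety: Incidence and severity of AEs and SAEs Tolerability: Dose interruptions, reductions and dose intensity". Its objective is to characterise safety and tolerability with food; no comparison, hypothesis or margin is attached.

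The measure itself is fixed elsewhere:

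- **Group 4 primary analysis (2.5.2.5):** "Frequencies of treatment-emergent AEs will be calculated to characterize the safety and tolerability of the study treatment". Section 2.5.2.6 refers to 2.8.1 for the method.
- **AE tables (2.8.1):** "AEs will be summarized by number and percentage of subjects having at least one AE", and "A subject with multiple occurrences of an AE will be counted only once in the respective AE category".
- **AESIs (2.8.1.1):** "the number and percentage of subjects with at least one event of the AESI occurring during the on-treatment period will be summarized".
- **Tolerability counts (2.4.1):** "The number (%) of subjects who have dose reductions or interruptions, and the reasons, will be summarized by treatment group".
- **Window (2.1.4):** first dose to 30 days after the last dose of either drug, with no fixed upper limit.
- **Denominator (2.1.3):** subjects, not subject-time.
- **Final CSR (2.5.2):** "The analyses described below will be updated including the data collected for subjects ongoing at the cutoff date for the primary analysis".

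Two provisions already reflect time on treatment. Dose intensity and relative dose intensity use each drug's own duration of exposure, and duration of exposure is tabulated by treatment group (both 2.4.1).

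**The concern.** A percentage of subjects ever having an event depends on the event risk and on how long subjects were observed. A subject who stops in week 3 without an event and one who is event-free after two years contribute identically.

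The groups have reason to differ in treatment time. Group 1 is TKI-resistant and in second to fourth line, Group 3 is first line, and Group 4 is a mixture with about 10 of about 30 subjects treatment-naive (1.1.2). Section 2.8 puts the safety tables side by side by treatment group, and Group 4 is the only fed group.

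The final CSR adds follow-up only for subjects still on treatment at the primary cut-off, that is, those already treated longest. Apart from recoding and data corrections, that moves the cumulative percentages upward. A reader could take either kind of difference as a difference in tolerability when it reflects duration.

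**Working it through.** **The plan's own figures.** The SAP states no AE rate, no exposure by group and no precision target, so the size cannot be reproduced from it. The group sizes in 1.1.2 do add up: 40 + 5 + 40 + 30 = 115, the stated Phase II total.

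**Assumed inputs.** The first-event hazard h is constant and identical in all groups. Treatment time is exponential with mean m months, followed by 1 month for the 30-day tail. Pretreated subjects have m = 6 and first-line subjects m = 15. From 1.1.2, Group 4 is weighted 20 pretreated to 10 naive.

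**Crude percentage:** P = 1 − exp(−h)/(1 + h·m).

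At h = 0.05:

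- m = 6: 1 − 0.9512/1.30 = 26.8%
- m = 15: 1 − 0.9512/1.75 = 45.6%
- Group 4: (20 × 26.8 + 10 × 45.6)/30 = 33.1%

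| h per month | Group 1 (m = 6) | Group 3 (m = 15) | Group 4 | Group 4 − Group 1 | Group 3 − Group 4 |
|---|---|---|---|---|---|
| 0.02 | 12.5% | 24.6% | 16.5% | 4.0 | 8.1 |
| 0.05 | 26.8% | 45.6% | 33.1% | 6.3 | 12.5 |
| 0.10 | 43.4% | 63.8% | 50.2% | 6.8 | 13.6 |

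Every gap in the table arises with no true difference in risk.

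**Other exposure assumptions.** Take a 5% risk per 4 weeks in every group, so h = −ln(0.95)/4 per week, and P = 1 − exp(−h·30/7)/(1 + h·m) with m in weeks.

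- Means of 24 and 78 weeks: Groups 1, 3 and 4 show 27.6%, 52.7% and 36.0%.
- Means of 40 and 60 weeks: 37.4%, 46.5% and 40.5%, so Group 4 differs by 3.1 and 6.0 points.

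**Early-onset events.** If the same hazard acts only in the first 8 weeks, the crude percentage is 9.8% for treatment of 8, 24, 52 or 78 weeks. There is no distortion.

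**The remedy under the same assumptions.** First events divided by subject-time at risk estimates h directly: 0.05 per month in both groups, or 0.05 × 12 × 100 = 60 per 100 subject-years.

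The cumulative incidence at 6 months, with end of the on-treatment period as a competing event, is 1 − exp(−h) + exp(−h) × [h/(h + 1/m)] × [1 − exp(−5(h + 1/m))].

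At h = 0.05:

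- m = 6: 0.0488 + 0.9512 × 0.2308 × 0.6615 = 19.4%
- m = 15: 0.0488 + 0.9512 × 0.4286 × 0.4420 = 22.9%

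The gap falls from 18.8 points to 3.5. It does not vanish, because fewer subjects remain at risk in the group that stops earlier.

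**The case against.** The strongest reply is that crude n (%) is a standard reading of incidence, that Group 4 is only to be characterised, and that duration of exposure is reported by group in the same Safety set. All three are true, and nothing in the SAP is contradicted. They do not remove the weakness: an exposure table shows that durations differ but does not let a reader convert an AE percentage.

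Several limits on the point stand.

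- **Unequal exposure is inferred.** The classes from 4 weeks or less to more than 78 weeks in 2.4.1 are table intervals, not data.
- **Precision is low.** At n = 30, an observed 50% (15/30) has an exact 95% interval of 31.3 to 68.7%, wider than the gaps shown.
- **Absence is of visible text only.** Parts of the safety section are redacted, Section 2.8.1.2 is cited but not shown, and the table shells are separate. Section 5.1.2 mentions analyses of time to AEs, and the amendment history records an earlier time-to-first-dose-modification analysis. Neither appears as a summary in the visible 2.4.1 or 2.8.1.

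Two stronger readings are tempting. A reader might infer that the whole Group 4 endpoint is a crude percentage, but dose intensity is already per day. A reader might also infer that crude percentages are what prevent the food condition from being judged. The SAP plans no fed-versus-fasted comparison. The groups are not randomised and differ in line of therapy, so such a contrast would stay confounded after exposure adjustment.

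**Conclusion.** The point holds as a limited, inexpensive improvement to the safety analysis. For events that accrue over time, the visible AE, AESI, reduction and interruption summaries cannot separate risk from duration, either between groups or between the primary and final CSR.

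The 18.8-point gap at a hazard of 0.05 per month is between two assumed exposure patterns resembling fasted Groups 1 and 3. It is not the size of any food contrast. For Group 4 the corresponding gaps are about 6 and 12.5 points, about 3 and 6 points if mean exposures are closer, and near zero for early-onset events. These sizes rest on a constant, common hazard and assumed exponential treatment times, since the SAP gives no exposure by group.

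**What to change.** Keep the n (%) tables. In Sections 2.8.1, 2.4.1 and 2.5.2.6 add the following by treatment group for any AE, grade 3 or higher AE, SAE, AE leading to discontinuation, each AESI, first dose reduction and first interruption:

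1. The exposure-adjusted incidence rate: subjects with a first event divided by subject-time from first dose to that event or the end of the on-treatment period.
2. The cumulative incidence at 6 cycles (about 6 months, the follow-up on which 1.1.2 timed the primary analysis), by the Aalen-Johansen estimator, with death and end of the on-treatment period without the event as competing events. One minus Kaplan-Meier would treat those exits as uninformative censoring and overstate the proportion affected.

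Show Group 4 also by treatment-naive versus pretreated. Section 1.1.2 enrols naive subjects there to collect safety information, while 2.2.2.3 plans no safety subgroup analyses, so that sentence needs an exception. State that any fed-versus-fasted difference is descriptive and confounded by line of therapy.

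The cost is SAP wording and a few tables from AE and dosing dates already collected. The rate assumes a roughly constant hazard, which the fixed-time estimate offsets. The fixed-time estimate ignores later events and still depends somewhat on early discontinuation, so the two should be read together.
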